## DOCUMENT HISTORY

Document	Date of Issue	Overall Rationale
MK-3475-598-06	11-DEC-2020	Data from IA1 of KEYNOTE-598 (data cutoff: 01-SEP-2020) indicated that the study did not meet the prespecified success criteria for improvement in PFS or OS for the combination of pembrolizumab plus ipilimumab compared with pembrolizumab plus placebo. Furthermore, a nonbinding futility analysis was performed at IA1 at the request of the eDMC. This analysis showed the study met the criteria for declaring futility and the benefit-risk assessment was not considered positive to continue the trial. Based upon these data and at the recommendation of the eDMC, MSD implemented this amendment to direct all ipilimumab and placebo administrations to stop, and to unblind the study. The study will remain open so ongoing subjects will have continued access to pembrolizumab.
MK-3475-598-05	14-JUL-2020	To update the assumptions and the timing of interim analyses (IA) in the Statistical Analysis Plan (SAP), and to include a Patient-reported Outcomes (PRO) secondary objective, endpoint, and statistical method for analysis.
MK-3475-598-04	14-FEB-2020	The primary reasons for this amendment is to update assumptions in the SAP.
MK-3475-598-03	15-FEB-2018	The primary reasons for this amendment were to add a new exploratory objective (Objective 8) to evaluate the immunogenicity, exposure, antidrug antibodies (ADA), and pharmacokinetic (PK) samples; to add a new Exclusion Criterion #25 "Has known ROS1 mutation: if treatment and testing for ROS1 is approved and accessible."; and to add required thyroid (TSH, FT3/T3, FT4/T4) and adrenal (ACTH) function monitoring before to each dose of ipilimumab/placebo. Other clarifications and minor revisions were also included.

Document	Date of Issue	Overall Rationale
MK-3475-598-02	4-DEC-2017	The primary reason for this amendment was to update the background information and rationale for the dose and regimen of ipilimumab based on input from regulatory agencies. Additional revisions and clarifications were made to align with the pembrolizumab program template and updated risk language.

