4.3	Benefit/Risk	Added note to clarify that the benefit-risk assessment of ipilimumab is no longer applicable and related text has been removed.	In accordance with the overall rationale for the amendment, the benefit/risk assessment of ipilimumab is no longer applicable.
5.2.3	Trial Blinding	Added note to clarify that blinding and emergency unblinding are no longer applicable. All subjects will receive open-label pembrolizumab monotherapy.	Ipilimumab and matching placebo have been removed from the study and the study has been unblinded.
7.1.4.2	Subject Blinding/Unblinding		

Section Numbers	Section Titles	Description of Changes	Rationale
5.10	Beginning and End of the Trial	Added language to state that upon study completion, subjects are discontinued and may be enrolled in a pembrolizumab extension study, if available.	Subjects may be enrolled in a pembrolizumab extension study upon study completion.
6	Trial Flow Chart	Revised tables to remove assessments/procedures specific to ipilimumab and placebo treatments. Added a clarifying note.	In accordance with the overall rationale for the amendment, all references to ipilimumab and placebo, as well as assessments/procedures specific to these treatments, are removed from the protocol.
7.1.5.6	Second Course Phase	Revised text to remove ipilimumab and placebo references, as well as assessments/procedures specific to these treatments. Added a clarifying note.	Ipilimumab and matching placebo have been removed from the study.
7.2.1	Definition of an Overdose for This Protocol and Reporting of Overdose to the Sponsor		
8	Statistical Analysis Plan	Added notes to clarify that a nonbinding futility analysis planned for IA2 was performed at IA1 at the request of the eDMC, the study has been unblinded, and no further prespecified analysis of primary and secondary endpoints will be performed.	In accordance with the overall rationale for the amendment.

Section Numbers	Section Titles	Description of Changes	Rationale
7.2.7	Data Monitoring Committee	Added a statement that no additional eDMC reviews will take place.	In accordance with the overall rationale for the amendment.
8.7.1	Interim Safety Analyses		
8.8.4	Safety Analyses		
5.1.2	Subject Inclusion Criteria	Added note to clarify that contraception is no longer required for male participants and sperm donation is acceptable.	Since ipilimumab have been removed from the study, male contraception is no longer required.

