**1.0 TRIAL SUMMARY**

Abbreviated Title	Phase 3 1L Study of Pembrolizumab ± Ipilimumab in NSCLC
Sponsor Product Identifiers	MK-3475 Pembrolizumab
Trial Phase	3
Clinical Indication	First-line treatment of Stage IV metastatic programmed cell death-ligand 1 (PD-L1) positive (TPS ≥50%) NSCLC
Trial Type	Interventional
Type of control	Active control with placebo NOTE: As of Amendment 06, active control with placebo has been removed.
Route of administration	Intravenous (IV)
Trial Blinding	Double-blind NOTE: As of Amendment 06, the study is unblinded.
Treatment Groups	Pembrolizumab (MK-3475) 200 mg IV every 3 weeks (Q3W) + ipilimumab 1 mg/kg IV every 6 weeks (Q6W)  OR Pembrolizumab (MK-3475) Q3W 200 mg IV + Placebo IV Q6W NOTE: As of Amendment 06, ipilimumab and matching placebo have been removed from the treatment groups. Subjects remaining on treatment will receive open-label pembrolizumab monotherapy as per protocol.
Number of trial subjects	Approximately 568 subjects will be enrolled.
Estimated duration of trial	The Sponsor estimates that the trial will require approximately 5 years from the time the first subject signs the informed consent until the last subject's last study-related phone call or visit.

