10. A female subject is eligible to participate if she is not pregnant (see Section 12.5), not breastfeeding, and at least one of the following conditions applies: (1) is not considered to be a woman of childbearing potential (WOCBP) as described in Section 12.5 or (2) is a WOCBP who agrees to follow the contraceptive guidance in Section 12.5 during the treatment period and for at least 120 days (corresponding to time needed to eliminate any study treatment(s) (MK and or any active comparator/combination).
11. A male subject must agree to use contraception as detailed in Section 12.5 of this protocol during the treatment period and for at least 120 days after the last dose of study treatment and refrain from donating sperm during this period.  

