**Note: As of amendment 06, contraception is no longer required for male participants. Sperm donation is also acceptable.**

### 5.1.3 Subject Exclusion Criteria

The subject must be excluded from participating in the trial if the subject:

1. Has received prior systemic chemotherapy/other targeted or biological antineoplastic therapy treatment for their Stage IV metastatic NSCLC.

Note: Treatment with chemotherapy and/or radiation as part of neoadjuvant/adjuvant therapy is allowed as long as therapy was completed at least 6 months prior to the diagnosis of metastatic disease.

2. Tumor harbors an *EGFR*-sensitizing (activating) mutation or an *ALK* translocation.

Note: *EGFR*-sensitizing mutations are those mutations that are amenable to treatment with tyrosine kinase inhibitors including erlotinib, gefitinib, or afatinib. Subjects with nonsquamous histologies will not be randomized until *EGFR* mutation status and/or *ALK* translocation status is available in source documentation at the site.

For subjects enrolled who are known to have a tumor of predominantly squamous histology, molecular testing for *EGFR* mutation and *ALK* translocation will not be required as this is not SOC and is not part of current diagnostic guidelines.

3. Is currently participating in or has participated in a trial of an investigational agent or has used an investigational device within 4 weeks prior to the first dose of trial treatment.

Note: Subjects who have entered the Follow-up Phase of an investigational trial may participate as long as it has been 4 weeks after the last dose of the previous investigational agent.

4. Has received prior therapy with an anti-PD-1, anti-PD-L1, or anti PD-L2 agent or with an agent directed to another stimulatory or coinhibitory T-cell receptor (eg, CTLA-4, OX-40, CD137).
5. Has received prior radiotherapy within 2 weeks of start of trial treatment or received lung radiation therapy of >30 Gy within 6 months of the first dose of trial treatment. Subjects

must have recovered from all radiation-related toxicities, not require corticosteroids, and not have had radiation pneumonitis. A 1-week washout is permitted for palliative radiation ( $\leq 2$  weeks of radiotherapy) to non-CNS disease.

6. The subject's NSCLC can be treated with curative intent with surgical resection, localized radiotherapy, or chemoradiation.

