13. Has a history of (noninfectious) pneumonitis that required systemic steroids or current pneumonitis/interstitial lung disease.
14. Has had an allogeneic tissue/solid organ transplant.
15. Has received a live vaccine within 30 days prior to the first dose of trial treatment. Examples of live vaccines include, but are not limited to, the following: measles, mumps, rubella, varicella/zoster (chicken pox), yellow fever, rabies, Bacillus Calmette-Guérin (BCG), and typhoid vaccine. Seasonal influenza vaccines for injection are generally killed virus vaccines and are allowed; however, intranasal influenza vaccines (e.g., FluMist®) are live attenuated vaccines and are not allowed.
16. Has an active infection requiring systemic therapy.
17. Has a known history of HIV infection. No HIV testing is required unless mandated by local health authority.
18. Has a known history of hepatitis B (defined as hepatitis B surface antigen [HBsAg] reactive) or known active hepatitis C virus (defined as hepatitis C virus (HCV) RNA [qualitative] is detected) infection.  
  
Note: no testing for hepatitis B and hepatitis C is required unless mandated by local health authority.
19. Has a known history of active tuberculosis (TB; *Bacillus Tuberculosis*).
20. Has a history or current evidence of any condition, therapy, or laboratory abnormality that might confound the results of the trial, interfere with the subject's participation for the full duration of the trial, or is not in the best interest of the subject to participate, in the opinion of the treating investigator.
21. Has known psychiatric or substance abuse disorders that would interfere with cooperating with the requirements of the trial.
22. Is, at the time of signing informed consent, a regular user (including "recreational use") of any illicit drugs or had a recent history (within the last year) of substance abuse (including alcohol).
23. Is pregnant or breastfeeding, or expecting to conceive or father children within the projected duration of the trial, starting with the Screening Visit (Visit 1) through 120 days after the last dose of pembrolizumab or 90 days after the last dose of ipilimumab.
24. Has severe hypersensitivity ( $\geq$  Grade 3) to pembrolizumab and/or any of its excipients and/or to ipilimumab and/or any of its excipients.

25. Subjects with known *ROS1* mutation: if treatment and testing for *ROS1* is approved and accessible.

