### **5.7.3 Pregnancy**

If a subject inadvertently becomes pregnant while on treatment with pembrolizumab, the subject will be immediately discontinued from study treatment. The site will contact the subject at least monthly and document the subject's status until the pregnancy has been completed or terminated. The outcome of the pregnancy will be reported to the Sponsor without delay and within 24 hours if the outcome is a serious adverse experience (eg, death, abortion, congenital anomaly, or other disabling or life-threatening complication to the mother or newborn). The study investigator will make every effort to obtain permission to follow the outcome of the pregnancy and report the condition of the fetus or newborn to the Sponsor. If a male subject impregnates his female partner, the study personnel at the site must be informed immediately and the pregnancy must be reported to the Sponsor and followed as described in Section 7.2.2 – Reporting of Pregnancy and Lactation to the Sponsor.

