### Contraception Requirements

#### Male Participants:

**NOTE: As of amendment 06, contraception is no longer required for male participants. Sperm donation is also acceptable.**

Male participants with female partners of childbearing potential are eligible to participate if they agree to one of the following during the protocol defined time frame in Section 5.1.2:

- Be abstinent from penile-vaginal intercourse as their usual and preferred lifestyle (abstinent on a long-term and persistent basis) and agree to remain abstinent
- Use a male condom plus partner use of a contraceptive method with a failure rate of <1% per year as described in [Table 18](#) when having penile-vaginal intercourse with a WOCBP who is not currently pregnant.

- Note: Men with a pregnant or breastfeeding partner must agree to remain abstinent from penile-vaginal intercourse or use a male condom during each episode of penile penetration.

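### The Amendment 06 notes waive male contraception and the sperm-donation ban for every man, with no condition on time since his last ipilimumab dose (minor safety wording).

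*Combined protocol and SAP*

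**What the plan says.** Inclusion criterion 11 in Section 5.1.2 sets the rule: "A male subject must agree to use contraception as detailed in Section 12.5". It runs through treatment and for at least 120 days after the last dose of study treatment, and bars sperm donation over the same period.

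The Amendment 06 note to that criterion lifts both requirements: "As of amendment 06, contraception is no longer required for male participants. Sperm donation is also acceptable". Section 12.5 repeats that "contraception is no longer required for male participants". Neither note mentions time since the last dose or distinguishes men by arm.

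The Summary of Changes gives the reason: "Since ipilimumab have been removed from the study, male contraception is no longer required". The Document History says of the same amendment that "MSD implemented this amendment to direct all ipilimumab and placebo administrations to stop".

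The only ipilimumab-specific interval in the document is in exclusion criterion 23 (Section 5.1.3). It bars subjects expecting to conceive or father children through 120 days after pembrolizumab "or 90 days after the last dose of ipilimumab".

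**The concern.** The stated reason makes ipilimumab the basis of the male rule. On that reasoning the relevant clock is each man's last exposure, and ending supply does not end exposure in a man dosed a few weeks earlier.

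Elsewhere the protocol ties its precautions to the last dose. Criterion 11 and exclusion 23 both do so, and criterion 10, for women, explains its 120 days by the time needed to eliminate study treatment. The amended text also carries past exposure forward for toxicity: Table 6 and Section 5.6.1 still cover ipilimumab given previously. The contraception notes have no such carry-over, and nothing in the document explains why the interval may be cut short.

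At stake is a short gap in which a recently dosed man is told that he may father a child or donate sperm while still inside an interval that the protocol had set. No efficacy or safety analysis is affected.

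**Working it through.** There is no plan figure to reproduce. The check is calendar arithmetic.

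**Inputs**
- Amendment 06 issue date: 11-DEC-2020 (Document History). Assumed here to be the date ipilimumab stopped.
- Ipilimumab interval: every 6 weeks, 42 days (Section 1.0).
- Post-dose intervals: 90 days after ipilimumab (exclusion 23) and 120 days after study treatment (criterion 11). The 120 days is counted here from the last ipilimumab dose.
- Lag L from the ipilimumab stop to the waiver taking effect at a site: not in the documents, so shown as a range.

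**Formula.** For a man whose last dose was d days before the stop (d = 0 to 42 for the last cycle), days left = max(0, W − d − L), with W = 90 or 120.

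| Lag L (days) | Days left of 90 | Days left of 120 |
|---|---|---|
| 0 | 48 to 90 | 78 to 120 |
| 30 | 18 to 60 | 48 to 90 |
| 48 | 0 to 42 | 30 to 72 |
| 60 | 0 to 30 | 18 to 60 |
| 90 | 0 | 0 to 30 |
| 120 | 0 | 0 |

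The 3-day dosing window (Section 5.2.2) takes d to 45 and the zero-lag ranges to 45 to 90 and 75 to 120.

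**Dates**
- Last dose 30-OCT-2020 (42 days before issue) + 90 = 28-JAN-2021.
- Last dose 11-DEC-2020 + 90 = 11-MAR-2021; + 120 = 10-APR-2021.
- 11-DEC-2020 − 90 = 12-SEP-2020. On the 90-day figure, a man last dosed on or before that date is unaffected even at zero lag. A man last dosed 43 to 89 days before the stop is outside the table but still inside 90 days at zero lag.

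**How many men.** The document gives no count. A rough order of magnitude, using planning assumptions:
- IA1 required about 12 months from last randomization (Section 8.7.2) and its data cutoff was 01-SEP-2020. By 11-DEC-2020 every subject was therefore about 15 or more months from randomization.
- Treatment is capped at about 24 months (Section 5.8.1). With uniform enrolment over 20 months and 568/2 = 284 per arm, 284 × (24 − 15)/20 ≈ 128 combination subjects were under the cap.
- Under the control PFS curve in Section 8.9, S(t) = 0.5 × 2^(−(t − 6.5)/14.5) after 6.5 months. This gives S(15) ≈ 0.33, S(24) ≈ 0.22 and a mean of about 0.27 between them. Then 128 × 0.27 ≈ 35 subjects, both sexes, progression-free.

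Toxicity stops lower this; treatment beyond progression could raise it. The nivolumab plus six-weekly ipilimumab cohort in Section 4.2.2.1.2 had a median ipilimumab duration of 3.4 months, which also points to a small group.

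**The case against.** The strongest reply is that no stated rule is broken. No passage sets a male contraception interval after ipilimumab alone. The 90 days comes from an entry criterion about fathering children, while the rule actually waived is 120 days after study treatment. The sponsor also drops the 120-day pembrolizumab interval, to which no objection is made here. If one clause may be retired, the documents alone do not show why the other may not. This stands as a limit: 90 days is the nearest ipilimumab-specific figure in the protocol, not a requirement.

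The second reply concerns timing. Section 12.1 requires IRB/ERC approval of significant changes before implementation, except those needed urgently for subject safety. Stopping ipilimumab could use that exception; relaxing contraception would ordinarily wait. A positive lag is therefore plausible, and zero lag is the extreme case.

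Third, new information may reach subjects through a revised consent form (Section 7.1.1.1.1). Consent pages are not in the copy reviewed, so a transition instruction there cannot be excluded. Partner pregnancies are still followed: "If a male subject impregnates his female partner, the study personnel at the site must be informed immediately" (Section 5.7.3). That detects a pregnancy but does not prevent one.

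A reader might infer that every man on ipilimumab was released inside the interval on 11-DEC-2020, or that partners were put at demonstrated risk. The documents support neither: they give no site-level stop or waiver dates, no count of men, and no evidence of harm through semen. None of these replies shows that the unconditional wording is right.

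**Conclusion.** The point holds as low-severity safety wording, worth considering. Followed literally, the two notes can end a precaution early for a man recently given ipilimumab, and the only reason given does not address residual exposure.

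Its size is bounded by the lag. On the 90-day figure, no man dosed in the last cycle has passed the interval before the waiver at lags under 48 days, and nobody is affected from 90 days. On criterion 11's 120 days, nobody is affected from 120 days. The gap closes by itself: if the last doses were given by the issue date, by 11-MAR-2021 or 10-APR-2021 respectively.

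This rests on dosing having continued up to the amendment, on the notes being applied as written, and on no transition instruction elsewhere. The number of men is unknown and probably small.

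**What to change.** Send sites a short letter promptly, then add to both notes (Sections 5.1.2 and 12.5): *For men who received ipilimumab, this applies only from 90 days after their last ipilimumab dose.* Criterion 11's 120 days is the more cautious alternative. The letter comes first because a text change awaiting IRB/ERC approval could take effect after most of the interval has passed. Section 8.2 says the study is unblinded to sites, so they can identify the men concerned.

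The cost is a letter, one sentence in each of two notes within a protocol revision, IRB/ERC approval and, where required locally, a consent addendum. The downside is that these men continue contraception and refrain from sperm donation for up to the chosen interval after their last ipilimumab dose. No visits or tests are added. Once every man is past that interval, no action is needed.

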## 5.2 Trial Treatment(s)

**NOTE: As of Amendment 06, ipilimumab and matching placebo have been removed from the study. This section has been updated accordingly.**

The treatment(s) to be used in this trial are outlined below in [Table 5](#).

Table 5 Trial Treatment

Trial Treatment Name	Dosage Formulation	Unit Dose Strength(s)	Dosage Level(s)	Route of Administration	Sourcing
Pembrolizumab	Solution for Infusion	25 mg / mL	200 mg Q3W	IV infusion	Central

Abbreviations: IV=intravenous; NA=not applicable; Q3W=every 3 weeks.

Trial treatment must begin as close to treatment allocation/randomization as possible but no more than three days later.

All trial treatments will be administered on an outpatient basis.

All supplies indicated in [Table 5](#) above will be provided centrally by the Sponsor or locally by the trial site, subsidiary or designee, depending on local country operational or regulatory requirements.

For any commercially available product that is provided by the trial site, subsidiary or designee every attempt will be made to source these supplies from a single lot/batch number. The trial site is responsible for recording the lot number, manufacturer, and expiry date for any locally purchased product as per local guidelines unless otherwise instructed by the Sponsor.

The investigator shall take responsibility for and shall take all steps to maintain appropriate records and ensure appropriate supply, storage, handling, distribution and usage of trial treatments in accordance with the protocol and any applicable laws and regulations.

### 5.2.1 Dose Selection/Modification

#### 5.2.1.1 Dose Selection (Preparation)

Details on the dose calculation, preparation, and administration are provided in the Pharmacy Manual.

Pembrolizumab will be administered as per the approved product labels.

The rationale for selection of doses to be used in this trial is provided in Section 4.0 – Background & Rationale. There are no specific calculations or evaluations required to be performed in order to administer the proper dose to each subject.

### 5.2.1.2 Dose Modification (Escalation/Titration/Other) and Toxicity Management

**NOTE: As of Amendment 06, text in this section relating to dose modification of ipilimumab/matching placebo is no longer applicable. This section has been updated accordingly.**

